5.1.2 Pembrolizumab (MK-3475)

Pembrolizumab will be administered on Day 1 of each 3-week treatment cycle after all procedures/assessments have been completed. Pembrolizumab may be administered up to 3 days before or after the scheduled Day 1 of each cycle due to administrative reasons (up to 5 days after randomization is permitted).

Note: Dosing interruptions are permitted in the case of medical/surgical events or logistical reasons (i.e., elective surgery, unrelated medical events, patient vacation and holidays) not related to study therapy. Patients should be placed back on study therapy within 3 weeks of the scheduled interruption. The reason for interruption should be documented in the patient's study record.

Pembrolizumab will be administered as a dose of 200 mg using a 30-minute IV infusion. Infusion timing should be as close to 30 minutes as possible; however, a window of minus 5 minutes and plus 10 minutes is permitted (i.e., infusion time is 25 to 40 minutes. Please refer to section 8.1.2 for compatible infusion set materials including the in-line filter.

Anetumab ravtansine will be given prior to pembrolizumab for the combination therapy

when given together.

No specific prophylactic medications are recommended for pembrolizumab. Full supportive care is recommended as per community standards of medical care as determined by the treating physician.

Infusion-related reactions have been reported with pembrolizumab. Infusion-related reactions may present as allergic reaction (hypersensitivity), serum sickness, infusion and infusion-like reactions, cytokine release syndrome, or anaphylaxis. Mild infusion reactions can generally be treated with interruption of the infusion and medical intervention including IV fluids, antihistamines, nonsteroidal anti-inflammatory drugs, acetaminophen, and narcotics as needed. More severe or life-threatening reactions may require vasopressors, corticosteroids, and epinephrine. If symptoms resolve within one hour of stopping drug infusion, the infusion may be restarted at 50% of the original infusion rate (e.g., from 100 mL/hr to 50 mL/hr). Otherwise dosing will be held until symptoms resolve and the subject should be premedicated for the next scheduled dose. In the case of severe or life-threatening reactions, subsequent doses of pembrolizumab should not be administered.

5.2 Phase 1 Study

Since this combination has not been studied to date, the first 6 patients treated at dose level 1 will be used as an early safety lead-in per Section 13.2. If 2 or more patients experience a dose-limiting toxicity (DLT) as defined below, then the starting dose level will be adjusted and additional cohorts may be evaluated at dose levels -1 and -2 in the safety lead-in stage as described in section 13.1.2. The acceptable DLT rate is 0.20.

5.2.1 Definition of Dose Limiting Toxicity (DLT)

The NCI-CTCAE version 5.0 will be used to assess toxicities. Dose limiting toxicities (DLT) will be defined as any of the following events possibly related to the study drugs that occur during the first 2 cycles of therapy (6 weeks):

- Non-resolving (within 6 weeks) grade ≥ 2 corneal ulcer
- Any grade ≥ 3 uveitis or non-resolving (within 6 weeks) grade 2 uveitis
- Any grade ≥ 3 pneumonitis or non-resolving (within 6 weeks) grade 2 pneumonitis
- Any treatment-related grade 4 adverse event or non-resolving (within 6 weeks) treatment-related grade 3 adverse event
- Infusion reaction or hypersensitivity to anetumab ravidansine not controlled by infusion rate reduction and anti-allergic prophylaxis.
- Grade 5 toxicity

The DLT period is during the first two cycles. Patients who (a) have been on treatment for at least 28 days and received at least 85% of the total prescribed dose of each drug (combined over the 2 cycles) or (b) have experienced a DLT, will be “DLT evaluable” and included in the dose de-escalation decisions. Non-evaluable patients will be replaced for DLT assessment.

Management and dose modifications associated with the above adverse events are outlined in Section 6.

Note: PRO-CTCAE data should not be used for determining attribution, dose modifications or reporting of serious adverse events.

5.3 Phase 2 Study

Patients will be randomized 1:1 to receive the safe dosing combination of anetumab ravtansine with pembrolizumab identified during phase 1 or pembrolizumab alone.

5.4 General Concomitant Medication and Supportive Care Guidelines

Supportive care is otherwise recommended per community standards and may include oral and parenteral anti-coagulation if deemed necessary by the treating physician's discretion; prophylactic anti-emetics such as 5-HT3 blocks (granisetron, ondansetron); bisphosphonates or denosumab; analgesics; beta-blockers or digoxin.

Medications or vaccinations specifically prohibited in the exclusion criteria are not allowed during the ongoing trial. If there is a clinical indication for any medication or vaccination specifically prohibited during the trial, discontinuation from trial therapy or vaccination may be required. The investigator should discuss any questions regarding this with CTEP. The final decision on any supportive therapy or vaccination rests with the investigator and/or the patient's primary physician; however, the decision to continue the patient on trial therapy or vaccination schedule requires the mutual agreement of the Investigator, CTEP, and the patient.

Acceptable Concomitant Medications: All treatments that the investigator considers necessary for a patient's welfare may be administered at the discretion of the investigator in keeping with the community standards of medical care. All concomitant medication will be recorded on the case report form (CRF) including all prescription, over-the-counter (OTC), herbal supplements, and IV medications and fluids. If changes occur during the trial period, documentation of drug dosage, frequency, route, and date may also be included on the CRF.

All concomitant medications received within 30 days before the first dose of study treatment and 30 days after the last dose of study treatment should be recorded. Concomitant medications administered after 30 days after the last dose of trial treatment should be recorded for serious adverse events (SAEs).

Prohibited concomitant medications are listed in the exclusion criteria, sections 3.31, 3.36 and 3.37. Patients who, in the assessment by the investigator, require the use of any of the aforementioned treatments for clinical management should be removed from the trial. Patients may receive other medications that the investigator deems to be medically necessary. The study team should check a frequently- updated medical reference for a list of drugs to avoid or minimize use of. Appendix B Patient Drug Information Handout and Wallet Card should be provided to patients.

There are no prohibited therapies during the post-treatment follow-up portion of the study.

5.5 Duration of Therapy

In the absence of treatment delays due to adverse event(s), treatment with anetumab ravtansine may continue for up to a maximum of 12 months and treatment with pembrolizumab (all groups) may continue for up to 24 months or until one of the following criteria applies:

- Disease progression; see sections 5.7 and 5.9.
- Intercurrent illness that prevents further administration of treatment
- Adverse event(s) which require(s) treatment discontinuation:
 - Any dosing interruption lasting >12 weeks with the following exceptions:
Dosing interruptions >12 weeks that occur for non-drug-related reasons may be allowed if approved by the Principal Investigator. Prior to re-initiating treatment in a patient with a dosing interruption lasting >12 weeks, the Principal Investigator must be consulted.
 - Tumor assessments should continue as per protocol even if dosing is interrupted.
- Patient decides to withdraw from the study
- General or specific changes in the patient's condition render the patient unacceptable for further treatment in the judgment of the investigator
- Clinical progression is defined as occurring when a patient's condition has deteriorated and the patient cannot continue with study treatment per the investigator's judgment regardless of imaging findings
- Patient non-compliance
- Pregnancy
 - All women of child bearing potential should be instructed to contact the investigator immediately if they suspect they might be pregnant (e.g., missed or late menstrual period) at any time during study participation.
 - The investigator must immediately notify CTEP in the event of a confirmed pregnancy in a patient participating in the study.
- Termination of the study by sponsor
- The drug manufacturer can no longer provide the study agent
- If a patient has had a confirmed complete response (CR) that have been treated for at least 24 weeks with pembrolizumab and has continued at least two cycles beyond complete response, discussion between the treating physician and investigator regarding discontinuation of study treatment may be considered.

The reason(s) for protocol therapy discontinuation must be documented in the Case Report Form (CRF).

5.6 Duration of Follow Up

Patients will be followed for 12 months after removal from study treatment or until death, whichever occurs first. Patients will be followed every three months by a telephone call or letter to assess vital status. Patients removed from study for unacceptable adverse event(s) will be followed longer if needed until resolution or stabilization of the adverse event.

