American Association for Cancer Research in 2015. Patients with MPM whose tumor cells had 1% or greater expression of PD-L1 were included as a cohort in a larger phase 1 clinical. Responses were measured by standard Response Evaluation Criteria in Solid Tumors (RECIST) version 1.1 every eight weeks. PD-L1 expression was detected in 38 patients of 84 who were screened (45%), and 25 of these patients were treated. There were three moderate to severe (grade 3 or higher) drug-related adverse events. There were six responders (24%, including unconfirmed responses) and 13 patients with stable disease (52%) for an impressive disease control rate of 76% (25). An update of this trial was presented at the 2016 International Association for the Study of Lung Cancer (IASLC) World Conference on Lung Cancer (WCLC) and the confirmed, clinical benefit rate (complete responses, partial responses and stable disease for six months or greater) was 40%, and the median overall survival was 18 months in this pretreated population (26).

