Pembrolizumab has also been used in MPM in a larger phase 2 clinical trial with a two-stage design. The interim results from this trial were also presented at the 2016 IASLC WCLC meeting. There were important differences between these two trial designs to consider, including the eligibility of patients without detectable PD-L1 expression, the flat dosing of pembrolizumab, less frequent imaging assessments, and the use of the modified pleural RECIST (27). There were 35 patients who enrolled but one subject withdrew. Two patients died on study because of autoimmune hepatitis and an unknown cause. At the time of the presentation, the median progression free survival (PFS) was 6.2 months and the median overall survival (OS) had not been reached. There were seven partial responses (21%) and 19 patients with stable disease (56%). Over half of the patients did not have detectable PD-L1 expression yet responses to pembrolizumab were seen regardless (28). Similarly, in the largest trial of PD-1/PD-L1 axis inhibition to date in MPM, avelumab, an anti-PD-L1 antibody, demonstrated an overall response rate of 9.4%, regardless of tumor cell PD-L1 expression (29). Both pembrolizumab and avelumab have been relatively well tolerated by patients with MPM or other cancers; however, they are commonly associated with rash and auto-immune-like conditions affecting the endocrine system. Most of these toxicities do not overlap with those of anetumab ravidansine. In contrast to PD-1/PD-L1 axis inhibitors, the CTLA-4 inhibitor tremelimumab showed no benefit compared to best supportive care in patients with MPM and was poorly tolerated (30). Overall, inhibition of PD-1/PD-L1 interaction is a promising therapeutic strategy in MPM that needs further validation as a single agent, and may be synergistic in combination with chemotherapy.

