5.7 Criteria for Removal from Study

Patients will be removed from study treatment when any of the applicable criteria, including confirmed progressive disease as the overall objective status (Section 11.1.5.3), adverse events, patient withdrawal or inability to follow study protocol as listed in Section 5.5. The reason for study removal and the date the patient was removed must be documented in the Case Report Form.

If radiologic imaging shows progressive disease (PD), tumor assessment should be repeated by the site \geq 4 weeks later in order to confirm PD with the option of continuing treatment while awaiting radiologic confirmation of progression as per section 5.9.

As per section 5.6 patients will be followed for 12 months after removal from study treatment or until death, whichever occurs first. Patients will be followed every three months by a telephone call or letter to assess vital status. Patients removed from study for unacceptable adverse event(s) will be followed longer if needed until resolution or stabilization of the adverse event.

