13.5.2 Overall Survival

Overall survival is defined as the time from the start of treatment to death due to any cause. The distribution of survival time will be estimated using the method of Kaplan-Meier. The comparison of overall survival between two treatment arms will be based on the log-rank test.

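### Vital-status follow-up ends 12 months after each patient stops treatment, so overall survival is censored by outcome after month 12 and is probably overstated by a small to moderate amount

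*Combined protocol and SAP*

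**What the plan says.** Section 5.6 sets the length of survival follow-up: "Patients will be followed for 12 months after removal from study treatment or until death, whichever occurs first". It also sets the method: "Patients will be followed every three months by a telephone call or letter to assess vital status". Section 5.7 repeats both.

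The event that starts this 12-month clock depends on outcome. Section 5.7 lists the reasons for ending treatment, "including confirmed progressive disease as the overall objective status", along with adverse events and withdrawal. Section 5.5 adds clinical deterioration and sets the longest treatment: "treatment with pembrolizumab (all groups) may continue for up to 24 months".

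The survival analysis runs on a different clock: "Overall survival is defined as the time from the start of treatment to death due to any cause" (13.5.2). Estimation is by Kaplan-Meier, and "The comparison of overall survival between two treatment arms will be based on the log-rank test". Section 13.5.1 gives a censoring date for duration of response; 13.5.2 gives none for overall survival, and no common cut-off or sensitivity analysis.

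**The concern.** How long a patient is followed for survival depends on how long disease control lasts. Patients who progress early and are still alive leave the risk set first. The later part of each curve then rests increasingly on patients with long disease control. Kaplan-Meier and log-rank both take those censored to have the same future risk as those who remain.

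The protocol's own background gives reason to doubt that. In the front-line trial re-analysed in section 2.3, patients with epithelioid disease who responded had a median survival of 20.6 months against 9.4 for non-responders (hazard ratio 0.341). PFS moved the same way, 7.8 against 3.7 months. The protocol cautions that this may not carry over to other therapies, but it makes independence hard to assume.

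The rule guarantees contact only to month 12. Section 2.2.2 reports for one pembrolizumab cohort that "the median overall survival was 18 months in this pretreated population". If survival here is similar, the median falls where the rule is already removing patients. Deaths that were never ascertained cannot be recovered by a later analysis.

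**Working it through.** The plan gives no event target, power or hazard ratio for overall survival, so there is no figure to reproduce. The check asks what the rule does to the planned estimates.

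**Inputs from the documents**
- Follow-up: 12 months after treatment ends (5.6, 5.7). Treatment cap: 24 months (5.5).
- Scans every 9 weeks (11.1.1); progression confirmed at least 4 weeks later (5.7, 5.9).
- "the median progression free survival (PFS) was 6.2 months" in one pembrolizumab trial, where median survival was not reached; median survival of 18 months in a different, PD-L1-positive cohort (both 2.2.2).
- Phase 2: 98 evaluable patients, about 34 months of accrual, final analysis at about 39.5 months (13.1.3.3, 13.3.2).

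**Step 1: when contact ends.** Censoring time C = time off treatment + 12 months.
- Off at the first scan: 63 days / 30.4375 = 2.1 months, so C = 14.1.
- Off after 4-week confirmation: 91 / 30.4375 = 3.0 months, so C = 15.0.
- Off at 6.2 months: C = 18.2. Off at 24 months: C = 36.

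**Step 2: who is affected before month 18.** These are patients off treatment before month 6 who outlive the window. With exponential PFS (median 6.2), 1 − 2^(−6/6.2) = 49% have progressed by month 6. If treatment stops at the next scan plus 4 weeks, 38% are off by then. Most of them die inside the window, so only 6–19% of all patients are censored alive before month 18.

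**Step 3: size of the bias.** Simulation with survival = PFS + post-progression survival (PPS). PFS is exponential with median 6.2 months; PPS is Weibull, scaled so that median survival is 18.0 months. The distributions, the PFS–PPS correlation and the pairing of medians from two trials are assumptions. Examples, with 1,000,000 patients each:

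| Correlation | PPS shape | Treatment stops at | Kaplan-Meier median (true 18.0) | 24-month survival: Kaplan-Meier / true | Difference, points | Deaths by month 24 missed |
|---|---|---|---|---|---|---|
| 0.3 | 1.0 | scan + 4 weeks | 18.34 | 0.3973 / 0.3655 | +3.2 | 11.1% |
| 0.3 | 0.7 | progression | 18.56 | 0.418 / 0.392 | +2.6 | 13.1% |
| 0 | 0.7 | progression | 18.16 | 0.384 / 0.377 | +0.7 | 13.8% |
| 0.3 | 0.5 | progression | 18.25 | 0.422 / 0.413 | +0.9 | 9.9% |
| 0 | 0.5 | progression | 17.83 | 0.385 / 0.399 | −1.4 | 10.4% |

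Over 12 scenarios (correlation 0 to 0.6, shape 0.7 or 1, either stopping rule), 24-month survival is 0.3 to 6.4 points too high and the median about 0 to 1.3 months too long. Deaths missed are 8–18% of those by month 24 and 20–30% of those by month 36. Widening the shape to 0.5–1.3 gives −1 to +7 points at 24 months. With scan-based stopping, the median is overstated by no more than about half a month.

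**Step 4: deaths at the planned analysis.** With uniform accrual and analysis at 39.5 months, a common cut-off would record about 53–56 deaths among 98 patients. The 12-month rule loses about 6–8 of them with scan-based stopping, and up to about 11 if treatment stops at progression itself.

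**Step 5: the first 12 months.** Time off treatment cannot be negative, so C is at least 12 and the rule censors nobody earlier. Patients entered after month 39.5 − 12 = 27.5 have less than 12 months of potential follow-up at the analysis: (34 − 27.5) / 34 = 19% under uniform accrual. That censoring comes from entry date and does not bias the estimate.

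**The case against.** The case for leaving the plan alone has weight. Overall survival is not among the objectives in 1.2 and has no power or event target; the go/no-go decision rests on response rate. A finite period of post-treatment contact is partly a resource choice. Treatment continues to the next scan and often through confirmation, which lengthens follow-up and shrinks the bias. The between-arm difference moved little in simulation. All of this stands and limits the severity. It does not remove the dependence of censoring on outcome, which follows from carrying out the plan exactly as written.

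Three stronger readings are tempting, and the documents do not support them.
- A reader might infer that about half of all deaths are missed. Taking 18 − 6.2 = 11.8 months as the median PPS gives 2^(−12/11.8) = 49% surviving beyond the window. But medians do not subtract: PPS scaled to a median survival of 18 months has a median of about 7–10 months in most scenarios. Even over unlimited follow-up, which no trial collects, the share missed is 34–45%.
- A reader might infer that early progressors as a group are lost before month 18. Most die within the window and are counted.
- A reader might infer that every curve is too high after month 12. The last row of the table shows a slight reversal when PPS is unrelated to PFS and its hazard falls steeply.

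**Conclusion.** The concern holds in a limited form. Sections 5.6 and 5.7 make survival follow-up depend on outcome, from about month 14–15 for the earliest progressors, and 13.5.2 applies methods that assume otherwise. The likely effect is an upward bias after month 12, of the size shown in steps 3 and 4 and towards the lower end when stopping follows the scan schedule. The direction is probable, not certain. The magnitude rests on medians from two external trials, neither a design assumption here, and on assumed distributions. Severity is low, because this is an unpowered secondary analysis that decides nothing. It still merits correction: the remedy is cheap and the lost deaths cannot be recovered later.

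**What to change.** In 5.6 and 5.7, replace the off-treatment clock with one rule for all patients: continue the existing three-monthly call or letter until death or a common calendar cut-off. A fixed time from randomization would also serve; 36 months would match the longest follow-up now possible. In 13.5.2, state that survivors are censored at that cut-off or at last contact, if earlier. The cost is a protocol amendment and some extra contacts by the method already in use.

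If follow-up cannot be extended, limit the overall survival estimates and comparison in 13.5.2 to the first 12 months from treatment start, and say that patients with shorter potential follow-up at the analysis are censored administratively. This needs only analysis wording; its cost is a shorter survival horizon.

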5.7 Criteria for Removal from Study

Patients will be removed from study treatment when any of the applicable criteria, including confirmed progressive disease as the overall objective status (Section 11.1.5.3), adverse events, patient withdrawal or inability to follow study protocol as listed in Section 5.5. The reason for study removal and the date the patient was removed must be documented in the Case Report Form.

If radiologic imaging shows progressive disease (PD), tumor assessment should be repeated by the site \geq 4 weeks later in order to confirm PD with the option of continuing treatment while awaiting radiologic confirmation of progression as per section 5.9.

As per section 5.6 patients will be followed for 12 months after removal from study treatment or until death, whichever occurs first. Patients will be followed every three months by a telephone call or letter to assess vital status. Patients removed from study for unacceptable adverse event(s) will be followed longer if needed until resolution or stabilization of the adverse event.

5.8 Criteria to Resume Treatment Following a Drug-Related Adverse Event

For non-autoimmune or inflammatory events, patients may resume treatment with study drug when the drug-related AE(s) resolve to \leq Grade 1 or baseline value, with the following exceptions:

- Patients may resume treatment in the presence of Grade 2 fatigue.
- Patients with baseline Grade 1 AST/ALT or total bilirubin who require dose delays for reasons other than a 2-grade shift in AST/ALT or total bilirubin may resume treatment in the presence of Grade 2 AST/ALT OR total bilirubin.
- Patients with combined Grade 2 AST/ALT AND total bilirubin values meeting study parameters outlined in Section 6.1 should have treatment permanently discontinued.
- Non-drug-related toxicity including hepatic, pulmonary toxicity, diarrhea, or colitis, must have resolved to baseline before treatment is resumed.
- Drug-related endocrinopathies (not including drug-related adrenal insufficiency or hypophysitis) adequately controlled with only physiologic hormone replacement may resume treatment after replacement correction and clinically stable regimen.

If the criteria to resume treatment are met, the patient should restart treatment no sooner than the next scheduled time point per protocol. However, if the treatment is delayed past the next scheduled time point per protocol, the treatment should resume at the earliest convenient point that is within the 12 week delay period.

If treatment is delayed >12 weeks, the patient must be permanently discontinued from study therapy, except as specified in Section 5.5 (Duration of Therapy).

Note: PRO-CTCAE data should not be used for determining treatment resumption following a drug-related symptomatic adverse event.

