6.2 Dose Modifications for Anetumab Ravtansine

Dose Level	Anetumab Ravtansine Dose
1	6.5 mg/kg
-1	5.5 mg/kg
-2	4.5 mg/kg

Neutrophil count decreased ^{1, 2}	Management/Next Dose
\leq Grade 1	No change in dose
Grade 2	No change in dose
Grade 3	Hold ² until $<$ Grade 2. Resume at one dose level lower.
Grade 4	Hold ² until $<$ Grade 2. Resume at one dose level lower.
1.	Patients with febrile neutropenia should hold ^{**} until $<$ grade 2 and resume at one dose level lower.
2.	G-CSF and other hematopoietic growth factors may be used during the study in the management of acute toxicity such as febrile neutropenia when clinically indicated per ASCO Recommendations for Therapeutic Use of CSF (63) or at the discretion of the investigator; however they may not be substituted for a required dose reduction.
3.	Patients requiring a delay of $>$ 12 weeks should go off protocol therapy.

Platelet count decreased¹	Management/Next Dose
≤ Grade 1	No change in dose
Grade 2	No change in dose
Grade 3	Hold ² until < Grade 2. Resume at one dose level lower.
Grade 4	Hold ² until < Grade 2. Resume at one dose level lower.
1.	Patients with active bleeding related to drug-induced thrombocytopenia should reduce by one dose level.
2.	Patients requiring a delay of > 12 weeks should go off protocol therapy.

Non-hematologic toxicities	Management/Next Dose
≤ Grade 1	No change in dose.
Grade 2	No change in dose.
Grade 3	Hold ¹ until ≤ Grade 2. Resume at same level or at one dose level lower, per investigator's discretion. ²
Grade 4	Off protocol therapy
1.	Patients requiring a delay of > 12 weeks should go off protocol therapy.
2.	Patients requiring > two dose reductions should go off protocol therapy.

Corneal Epitheliopathy	Definition	Management/Next Dose^{1, 2}
Grade 0	No pathologic changes	No change in anetumab ravtansine; ocular lubricants at discretion of investigator or ophthalmologist
Grade 1	Any stage of superficial punctate keratitis (SPK; as per the Oxford Schema for grading SPK from stage 0 to IV)	No change in anetumab ravtansine; ocular lubricants; add topical steroids if SPK shows treatment emergent progression by ≥ 2 SPK grades

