4. If pembrolizumab has been withheld, pembrolizumab may resume after the irAE decreased to \leq Grade 1 after corticosteroid taper.

irAEs	Toxicity grade (CTCAE V5.0)	Action with pembrolizumab	Corticosteroid and/or other therapies	Monitoring and follow-up
Pneumonitis	Grade 2	Withhold	
 • Administer corticosteroids (initial dose of 1 - 2 mg/kg prednisone or equivalent) followed by taper • Add prophylactic antibiotics for opportunistic infections 	
 • Monitor participants for signs and symptoms of pneumonitis • Evaluate participants with suspected pneumonitis with radiographic imaging and initiate corticosteroid treatment
	Recurrent Grade 2, Grade 3 or 4	Permanently discontinue		
Diarrhea / Colitis	Grade 2 or 3	Withhold	
 • Administer corticosteroids (initial dose of 1 - 2 mg/kg prednisone or equivalent) followed by taper 	
 • Monitor participants for signs and symptoms of enterocolitis (ie, diarrhea, abdominal pain, blood or mucus in stool with or without fever) and of bowel perforation (ie, peritoneal signs and ileus) • Participants with \geqGrade 2 diarrhea suspecting colitis should consider GI consultation and performing endoscopy to rule out colitis • Participants with diarrhea/colitis should be advised to drink liberal quantities of clear fluids. If sufficient oral fluid intake is not feasible, fluid and electrolytes should be substituted via IV infusion
	Recurrent Grade 3 or Grade 4	Permanently discontinue		
AST or ALT elevation or Increased Bilirubin	Grade 2 ^a	Withhold	
 • Administer corticosteroids (initial dose of 0.5 - 1 mg/kg prednisone or equivalent) followed by taper 	
 • Monitor with liver function tests (consider weekly or more frequently until liver enzyme value returned to baseline or is stable)
	Grade 3 ^b or 4 ^c	Permanently discontinue	
 • Administer corticosteroids (initial dose of 1 - 2 mg/kg prednisone or 	

			equivalent) followed by taper	

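### Sections 5.8 and 6.2 set different restart thresholds for anetumab ravtansine after some drug-related Grade 3 non-hematologic toxicities, and neither is given precedence

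*Combined protocol and SAP*

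**What the plan says.** Section 5.8 (Criteria to Resume Treatment Following a Drug-Related Adverse Event) speaks of study drug in general and names neither agent: "patients may resume treatment with study drug when the drug-related AE(s) resolve to" a stated level. Its main rule is that events must "resolve to \leq Grade 1 or baseline value, with the following exceptions". Two of the exceptions permit a residual Grade 2 event:

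- Fatigue: "Patients may resume treatment in the presence of Grade 2 fatigue".
- Liver tests: patients with Grade 1 values at baseline, whose delay has a cause other than a two-grade shift in those values, "may resume treatment in the presence of Grade 2 AST/ALT OR total bilirubin".

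Section 5.8 also makes separate provision for controlled endocrinopathies.

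Section 6.2 covers anetumab ravtansine only. Its non-hematologic table holds a Grade 3 toxicity "until ≤ Grade 2. Resume at same level or at one dose level lower", with the choice of restart level left to the investigator. The neutrophil table in the same section uses a stricter threshold for Grades 3 and 4, "until $<$ Grade 2. Resume at one dose level lower", and the platelet table uses the same threshold.

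Section 6.3, for immune-related events on pembrolizumab, says "pembrolizumab may resume after the irAE decreased to \leq Grade 1 after corticosteroid taper".

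Sections 5.8 and 6.2 both end protocol therapy after a delay of more than 12 weeks. The exception in Section 5.5 is for interruptions that are not drug-related.

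**The concern.** Both sections tell a site when it may re-treat after a drug-related toxicity, and they use different grades. If both apply to the same event, the decision depends on which page the site consults.

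The first thing at stake is patient safety, since this is the restart rule for the experimental agent. The second is uniform conduct: hold lengths, dose intensity and discontinuations among patients on the combination could vary by site for a reason unrelated to the patient. The 12-week limit sharpens this, because a disagreement about the threshold can become a disagreement about whether the patient stays on treatment at all.

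**Working it through.** No arithmetic applies. The check is to apply both rules to the same patient.

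Take a patient on anetumab ravtansine with a drug-related Grade 3 non-hematologic event that is not immune-related, corneal or infusion-related. Treatment is held under Section 6.2. As the event improves:

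| State of the event | Section 5.8 | Section 6.2 | Agree? |
|---|---|---|---|
| Still Grade 3 | Do not resume | Do not resume | Yes |
| Grade 2, and the event is fatigue | May resume | May resume | Yes |
| Grade 2, and Grade 2 is the patient's baseline | May resume | May resume | Yes |
| Grade 2, above baseline, no 5.8 exception | Do not resume | May resume | **No** |
| Grade 1 or less | May resume | May resume | Yes |

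One row conflicts. Four further checks bear on whether it can be explained away.

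1. **Can the two rules be read as one?** Section 5.8 lists Grade 2 fatigue as an exception. If residual Grade 2 were generally acceptable, that exception would be unnecessary.
2. **Is the difference general to Section 6.2?** No. The neutrophil and platelet tables wait for less than Grade 2, that is Grade 1 or less, which matches Section 5.8. The mismatch is confined to the non-hematologic table.
3. **Does a cross-reference settle it?** No. Section 5.8 does not exempt the Section 6.2 table, and Section 6.2 does not mention Section 5.8. For combined liver values Section 5.8 sends the reader to parameters in Section 6.1, but Section 6.1 contains only a statement on PRO-CTCAE data.
4. **What happens at 12 weeks?** Suppose the event reaches Grade 2 within the 12 weeks and stays there. Under Section 6.2 treatment may restart. Under Section 5.8 the criterion is never met, the delay passes 12 weeks, and the patient is permanently discontinued.

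Section 6.4 adds a complication. When a toxicity is possibly related to either agent, both are held. For events outside the immune-related rules of Section 6.3, Section 5.8 is the section that gives a restart criterion for pembrolizumab. After one shared hold, the two agents could therefore have different restart thresholds.

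**The case against.** The strongest reply is that the specific rule governs. Section 5.1 says that dose modifications are described in Section 6. Footnote 1 to the phase 2 dose schedule sends modifications and holds for both agents there, and Section 5.2.1 does the same for managing dose-limiting toxicities. Section 6.2 is specific to agent and grade, and a site could reasonably follow it for anetumab ravtansine. This has weight, but none of these pointers says that Section 6 overrides the resumption criteria of Section 5.8, which is the section titled for that purpose. Nor does the text limit Section 5.8 to pembrolizumab.

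A second reply is that exposure already varies, because the same row of Section 6.2 leaves the restart level to the investigator, and Section 6.4 allows hold decisions to be discussed with the Principal Investigator. That is fair. It limits how much variation can be blamed on the conflict, but it does not tell a site which threshold applies.

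A third reply concerns scope, and it stands. A reader might infer that every Grade 3 non-hematologic event that improves only to Grade 2 is affected. The documents do not support that:

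- Grade 2 fatigue and a conditional liver-test case are excepted in Section 5.8, and controlled endocrinopathies are provided for there.
- Corneal epitheliopathy has its own table in Section 6.2.
- Infusion and hypersensitivity reactions to anetumab ravtansine have a restart rule in Section 5.1.1.
- Immune-related events fall under Section 6.3.
- Section 3.3.2 admits patients with neuropathy up to Grade 2. If that is their baseline, the rules agree.

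**Conclusion.** The inconsistency is real and narrow. It arises for phase 1 and phase 2 Group 2 patients whose drug-related Grade 3 non-hematologic event has improved to Grade 2, remains above baseline, and falls under none of the exceptions or separate rules above. For those patients the two sections give opposite instructions.

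Its frequency cannot be stated. Section 7.1.1 lists nausea and anorexia as likely (more than 20%) with anetumab ravtansine, and Section 5.8 excepts neither at residual Grade 2. Those rates are not rates of Grade 3 events that improve only to Grade 2.

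Two stronger readings do not hold. One is that only the randomized combination group is concerned: phase 1 patients received the same combination, and Section 6.4 treats them together with Group 2. The other is that the primary comparison is compromised. The protocol does call the dose-response of anetumab ravtansine very steep (Sections 2.2.1 and 2.3.2.1), so uneven delays could in principle affect response. With no frequency given, nothing in the documents shows a material effect. The response definition, its denominator, the significance level, the power and the sample size are unchanged.

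The conclusion assumes that Section 5.8 means what it says in referring to study drug without naming an agent.

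**What to change.** The sponsor should reconcile Section 5.8 with the Section 6.2 non-hematologic table so that one restart threshold applies, or state an explicit order of precedence by agent. The wording should also say what applies when both agents were held for the same event under Section 6.4. The Section 5.8 reference to Section 6.1 should be corrected in the same change. Which threshold is right is a clinical decision on which no view is taken here.

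The cost is amendment wording. Sample size, analysis and data collection do not change.
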